Appendix

1. Screening PHQ-9
2. Baseline CRF
3. 72 Hour Call CRF
4. 30 Day Call CRF
5. 90 Day Visit CRF

1. Screening PHQ-9

PATIENT HEALTH QUESTIONNAIRE (PHQ-9)

NAME: _____ DATE: _____

Over the last 2 weeks, how often have you been
bothered by any of the following problems?
(use "✓" to indicate your answer)

	Not at all	Several days	More than half the days	Nearly every day
1. Little interest or pleasure in doing things	0	1	2	3
2. Feeling down, depressed, or hopeless	0	1	2	3
3. Trouble falling or staying asleep, or sleeping too much	0	1	2	3
4. Feeling tired or having little energy	0	1	2	3
5. Poor appetite or overeating	0	1	2	3
6. Feeling bad about yourself—or that you are a failure or have let yourself or your family down	0	1	2	3
7. Trouble concentrating on things, such as reading the newspaper or watching television	0	1	2	3
8. Moving or speaking so slowly that other people could have noticed. Or the opposite—being so fidgety or restless that you have been moving around a lot more than usual	0	1	2	3
9. Thoughts that you would be better off dead, or of hurting yourself	0	1	2	3

add columns + +

(Healthcare professional: For interpretation of TOTAL, TOTAL: _____
please refer to accompanying scoring card).

10. If you checked off any problems, how difficult have these problems made it for you to do your work, take care of things at home, or get along with other people?	Not difficult at all _____
	Somewhat difficult _____
	Very difficult _____
	Extremely difficult _____

NOTE: SUBJECTS MUST SCORE BETWEEN 5-19, INCLUSIVE, TO BE ENROLLED

2. Baseline Study CRF (FOR ENROLLED PATIENTS ONLY):

1. **Subject ID #:** _____

2. **Enrolling Investigator:** _____

3. **Age:** ____

4. **Sex:** Male Female

5. **Race:** **(Check one)**

Caucasian
African American
Asian
American Indian
or Alaskan Native
Other

6. **Ethnicity:** Not Hispanic/Latino Hispanic/Latino

7. **Educational attainment**

Less than 9th grade
 9-11th grade (includes 12th grade with no diploma)
 High school graduate/GED or equivalent
 Some college or AA degree
 College graduate or above
 Refused

8. **Health insurance** (select all that apply)

Medicare
 Medicaid
 Veteran's Health Administration
 Private
 Other
 No insurance

9. **Symptom onset:** Witnessed onset Last known normal

Date: ____ / ____ / 20 ____ **Time:** ____ : ____
month day hr hr min min

10. **Medical History/Risk Factors:** **(Check all that apply)**

a. Hypertension	No  Yes 
b. Diabetes	No  Yes 
c. CAD	No  Yes 
d. Atrial Fibrillation	No  Yes 
e. CHF	No  Yes 
f. Prior TIA	No  Yes 
g. Prior Stroke	No  Yes 
h. Prior Anxiety	No  Yes 

- i. Prior Major Depressive Episode No Yes
- j. Prior PTSD No Yes
- l. Other (Please List):

11. **Tobacco** Never Former Current

12. **Current Alcohol** No Yes

If Yes, number of drinks per week: ___

13. **Marital Status:**

- Currently Married
- Divorced
- Widowed
- Never Married

14. **Number of People that you currently live with:** ___

15. **Were you working prior to this stroke?**

No Part Time Full Time

16. **Prior to the stroke, were you ever on a prescription medication for anxiety, depression, or PTSD?**

No Yes

If Yes, please list: _____

17. **Prior to the stroke did you ever participate in psychotherapy or counseling with a therapist?**

No Yes

18. **Stroke Location (check all that apply):**

- Right hemisphere
- Left hemisphere
- Posterior circulation
- Cortical
- Subcortical

19. **Vascular Territory of Stroke (check all that apply)**

ACA

- MCA
- PCA
- ICA
- Vertebral/Basilar

20. Stroke Etiology:

Free Text Description: _____

Stroke etiology at discharge (TOAST Criteria):

	Large Vessel Stenosis	
	Lacunar	
	Cryptogenic	
	Other: _____	

21. Discharge Disposition from Acute Hospitalization

Home
Acute Rehabilitation facility

22. Is the subject currently on pharmacotherapy for depression? (Review current medications)

- No
- Yes

If Yes, please list and select category from below: _____

- SSRI
- SNRI
- TCA
- Other

23. Abbreviated Duke Social Support Scale

Question	Answer		
Number of family members within 1 hour that you can depend on or feel close to?	None (1)	1-2 people (2)	More than 2 people (3)
Number of times in the past week in which you spent time with someone not living with you?	None (1)	1-2 times (2)	More than 2 times (3)
Number of times in the past week that you talked with friends/relatives on the telephone?	0-1 times (1)	2-5 times (2)	More than 5 times (3)
Number of times in the past week that you attended meetings of clubs, religious groups, or other groups that you belong to (other than at work)?	0-1 times (1)	2-5 times (2)	More than 5 times (3)
Do family and friends understand you?	Hardly ever (1)	Some of the time (2)	Most of the time (3)
Do you feel useful to family and friends?	Hardly ever (1)	Some of the time (2)	Most of the time (3)
Do you know what is happening with family and friends?	Hardly ever (1)	Some of the time (2)	Most of the time (3)
Do you feel listened to by family and friends?	Hardly ever (1)	Some of the time (2)	Most of the time (3)
Do you feel you have a definite role in family and among friends?	Hardly ever (1)	Some of the time (2)	Most of the time (3)
Can you talk about your deepest problem?	Hardly ever (1)	Some of the time (2)	Most of the time (3)
How satisfied are you with relationships with family and friends?	Very dissatisfied (1)	Somewhat dissatisfied (2)	Satisfied (3)

24. NIHSS

Date: month / day / 20 year

1a. Level of consciousness
 
0 alert 1 drowsy 2 stuporous 3 coma
 
1b. LOC questions (month, age)
 
0 both correct 1 one correct 2 incorrect
 
1c. LOC commands (close eyes, make a fist)
 
0 both correct 1 one correct 2 incorrect
 
2. Best gaze
 
0 normal 1 partial gaze palsy 2 forced deviation
 
3. Visual fields
 
0 no visual loss 1 partial hemianopia 2 complete hemianopia 3 bilateral hemianopia
 
4. Facial palsy
 
0 normal 1 minor 2 partial 3 complete
 
5. Motor arm
 
a. Left arm
 
0 no drift 1 drift 2 can't resist gravity 3 no effort against gravity 4 no movement Z amputation/joint fusion
 
b. Right arm
 
0 no drift 1 drift 2 can't resist gravity 3 no effort against gravity 4 no movement Z amputation/joint fusion
	
6. Motor leg
 
a. Left leg
 
0 no drift 1 drift 2 can't resist gravity 3 no effort against gravity 4 no movement Z amputation/joint fusion
 
b. Right leg
 
0 no drift 1 drift 2 can't resist gravity 3 no effort against gravity 4 no movement Z amputation/joint fusion
 
7. Limb ataxia (FNF, HKS)
 
0 absent 1 present in one limb 2 present in 2 limbs
 
8. Sensation (pin)
 
0 normal 1 partial loss 2 severe loss
 
9. Best language
 
0 no aphasia 1 mild-mod aphasia 2 severe aphasia 3 mute
 
10. Dysarthria
 
0 none 1 mild-mod 2 near to unintelligible or worse/mute Z intubated/barrier
 
11. Extinction and inattention
 
0 no neglect 1 partial neglect 2 complete neglect
 
Total Score: _____

---	--

25. Modified Rankin Scale

Score	Description
0	No symptoms at all
1	No significant disability despite symptoms; able to carry out all usual duties and activities
2	Slight disability; unable to carry out all previous activities, but able to look after own affairs without assistance
3	Moderate disability; requiring some help, but able to walk without assistance
4	Moderately severe disability; unable to walk without assistance and unable to attend to own bodily needs without assistance
5	Severe disability; bedridden, incontinent and requiring constant nursing care and attention
6	Dead

TOTAL (0–6): _____

26. Euro-QOL-5D

Please indicate which statements best describe your own health state today.
Mobility

I have no problems in walking about
 I have some problems in walking about
 I am confined to bed

Self-Care

I have no problems with self-care
 I have some problems washing or dressing myself
 I am unable to wash or dress myself

Usual Activities (e.g. *work, study, housework, family or leisure activities*)

I have no problems with performing my usual activities
 I have some problems with performing my usual activities
 I am unable to perform my usual activities

[figure not shown]
Pain/Discomfort

I have no pain or discomfort
 I have moderate pain or discomfort
 I have extreme pain or discomfort

Anxiety/Depression

I am not anxious or depressed

I am moderately anxious or depressed
 I am extremely anxious or depressed

Now, please write the number you marked on the scale in the box below.

YOUR HEALTH TODAY =

27. Internet/Mobile Device Usage

How do you access the internet? (Select all that apply):

- Computer
- Tablet
- Smart Phone

What is your preferred method of internet access? (Select 1):

- Computer
- Tablet
- Smart Phone

Where do you typically access the internet? (Select all that apply):

- Work
- Home
- Friend/Family member's home
- Public access point (i.e. Library, coffee shop, etc)
- Other: _____

Where is your preferred location to access the internet? (Select 1):

- Work
- Home
- Friend/Family member's home
- Public access point (i.e. Library, coffee shop, etc)
- Other: _____

How often do you typically access the internet? (Select 1):

- More than once a day
- Once a day
- Every couple of days
- Once a week or less

How much time per day do you typically spend on the internet?

- <30 minutes
- 30-59 minutes
- 60-119 minutes
- 120+ minutes

If you have a smartphone or tablet, do you use “Apps?”

- No
- Yes
- Not Applicable - do not own a smartphone or tablet

If you have a smartphone or tablet, do you ever have problems using it (e.g. typing, reading, using the touchscreen)?

- No
- Yes
- Not Applicable - do not own a smartphone or tablet

Have you ever used an “App,” website, or online platform to improve your health before?

- No
- Yes

If yes, how would you rate the experience?

- Not helpful
- Somewhat helpful
- Very helpful
- Not applicable

3. 72-Hour Phone Call

Date: ____ / ____ / ____
day day year

Does the patient have difficulty accessing Joyable? No ⁰ Yes ¹
If yes, please specify what the problem was and how it was addressed:

Name of the person who completed 48 hour follow up:

Signature: _____

Date: ____ / ____ / ____
month day year

4. 30-Day Phone Call

Date: ____ / ____ / ____
day day year

Does the patient have difficulty accessing Joyable? No ⁰ Yes ¹
If yes, please specify what the problem was and how it was addressed:

Name of the person who completed 48 hour follow up:

Signature: _____

Date: ____ / ____ / ____
month day year

1. Is the subject currently on pharmacotherapy for depression? (Review current medications)

No
 Yes

If Yes, please list and select category from below: _____

- SSRI
- SNRI
- TCA
- Other

2. Modified Rankin Scale

Score	Description
0	No symptoms at all
1	No significant disability despite symptoms; able to carry out all usual duties and activities
2	Slight disability; unable to carry out all previous activities, but able to look after own affairs without assistance
3	Moderate disability; requiring some help, but able to walk without assistance
4	Moderately severe disability; unable to walk without assistance and unable to attend to own bodily needs without assistance
5	Severe disability; bedridden, incontinent and requiring constant nursing care and attention
6	Dead

TOTAL (0–6): _____

2. Euro-QOL-5D

Please indicate which statements best describe your own health state today.
Mobility

____ I have no problems in walking about
 ____ I have some problems in walking about
 ____ I am confined to bed

Self-Care

____ I have no problems with self-care
 ____ I have some problems washing or dressing myself
 ____ I am unable to wash or dress myself

Usual Activities (e.g. work, study, housework, family or leisure activities)

____ I have no problems with performing my usual activities
 ____ I have some problems with performing my usual activities

I am unable to perform my usual activities

Pain/Discomfort

I have no pain or discomfort

I have moderate pain or discomfort

I have extreme pain or discomfort

Anxiety/Depression

I am not anxious or depressed

I am moderately anxious or depressed

I am extremely anxious or depressed

Visual Analogue Scale

Please indicate on this scale how good or bad your own health state is today.

The best health state you can imagine is marked 100 and the worst health state you can imagine is marked 0.

Please draw a line from the box to the point on the scale that indicates how good or bad your health state is today.

Your
own
health
state
today

Best imaginable
health state

Worst imaginable
health state

Now, please write the number you marked on the scale in the box below.

YOUR HEALTH TODAY =

5. 90 Day Visit

Date: month / day / 20 year

1. Is the subject currently on medications for depression? (Review current medications)

- No
- Yes

If Yes, please list and select category from below: _____

- SSRI
- SNRI
- TCA
- Other

2. Since enrolling in this study did you participate in psychotherapy or counseling with a therapist OTHER THAN what was provided through Joyable?

- No
- Yes

3. Are you currently working? No Part Time Full Time

3. NIHSS

1a. Level of consciousness
 
0 alert 1 drowsy 2 stuporous 3 coma
 
1b. LOC questions (month, age)
 
0 both correct 1 one correct 2 incorrect
 
1c. LOC commands (close eyes, make a fist)
 
0 both correct 1 one correct 2 incorrect
 
2. Best gaze
 
0 normal 1 partial gaze palsy 2 forced deviation
 
3. Visual fields
 
0 no visual loss 1 partial hemianopia 2 complete hemianopia 3 bilateral hemianopia
 
4. Facial palsy
 
0 normal 1 minor 2 partial 4 complete
 
5. Motor arm
 
a. Left arm
 
0 no drift 1 drift 2 can't resist gravity 3 no effort against gravity 4 no movement Z amputation/joint fusion
 
b. Right arm
 
0 no drift 1 drift 2 can't resist gravity 3 no effort against gravity 4 no movement Z amputation/joint fusion
	
6. Motor leg
 
a. Left leg
 
0 no drift 1 drift 2 can't resist gravity 3 no effort against gravity 4 no movement Z amputation/joint fusion
 
b. Right leg
 
0 no drift 1 drift 2 can't resist gravity 3 no effort against gravity 4 no movement Z amputation/joint fusion
 
7. Limb ataxia (FNF, HKS)
 
0 absent 1 present in one limb 2 present in 2 limbs
 
8. Sensation (pin)
 
0 normal 1 partial loss 2 severe loss
 
9. Best language
 
0 no aphasia 1 mild-mod aphasia 2 severe aphasia 3 mute
 
10. Dysarthria
 
0 none 1 mild-mod 2 near to unintelligible or worse/mute Z intubated/barrier
 
11. Extinction and inattention
 
0 no neglect 1 partial neglect • complete neglect

	
Total Score: _____

3. Modified Rankin Scale

Score	Description
0	No symptoms at all
1	No significant disability despite symptoms; able to carry out all usual duties and activities
2	Slight disability; unable to carry out all previous activities, but able to look after own affairs without assistance
3	Moderate disability; requiring some help, but able to walk without assistance
4	Moderately severe disability; unable to walk without assistance and unable to attend to own bodily needs without assistance
5	Severe disability; bedridden, incontinent and requiring constant nursing care and attention
6	Dead

TOTAL (0–6): _____

4. Euro-QOL-5D

Please indicate which statements best describe your own health state today.
Mobility

I have no problems in walking about
 I have some problems in walking about
 I am confined to bed

Self-Care

I have no problems with self-care
 I have some problems washing or dressing myself
 I am unable to wash or dress myself

Usual Activities (e.g. work, study, housework, family or leisure activities)

[figure not shown]
I have no problems with performing my usual activities
 I have some problems with performing my usual activities
 I am unable to perform my usual activities

Pain/Discomfort

I have no pain or discomfort
 I have moderate pain or discomfort
 I have extreme pain or discomfort

Anxiety/Depression

I am not anxious or depressed
 I am moderately anxious or depressed
 I am extremely anxious or depressed

YOUR HEALTH TODAY =

5. Healthcare Utilization

Since study enrollment:

How many times did you visit a **physician**? Do **not** include visits while in the hospital or to a hospital emergency room. Fill in with “0” or another number. _____ times

How many times did you go to a **hospital** emergency room? Fill in with “0” or another number. _____ times

How many different **times** did you stay in a hospital **overnight** or longer in the past 6 months? Fill in with “0” or another number. _____ times

How many total **nights** did you spend in the hospital? Fill in with “0” or another number. _____ nights

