Secondary outcome variables will include: completion of the iCBT program, number of telephone/email based coaching interactions, quality of life, measured using the EuroQOL-5D

(EQ-5D), healthcare utilization, measured using the Stanford Health Care Utilization Survey, and subject satisfaction with the program.

Background

Depression after stroke

Depression is common after stroke, occurring in up to one-third of all stroke patients.¹ A recent American Heart Association (AHA) scientific statement on post-stroke depression highlighted the importance of this condition, noting that it was “under-recognized, under-investigated, and under-treated.”² Individuals with depression after stroke have been shown to have lower functional status and lower quality of life than those without depression, irrespective of stroke severity, although the independent contribution of depression on outcomes is still not fully understood.

Traditional Cognitive Behavioral Therapy

Cognitive behavioral therapy (CBT) is an effective treatment for common mood disorders. Studies have shown a beneficial effect of CBT for both the treatment and prevention of depression after stroke.^{3,4} There is also evidence suggesting that CBT may provide a more durable and lasting treatment effect than pharmacotherapy with selective serotonin reuptake inhibitors.⁵

Despite the promise of CBT, its role in routine clinical practice is limited. There are significant barriers to widespread use of CBT. First, access to experienced CBT practitioners is limited.⁶ Second, the time and travel requirements to complete a course of CBT, which may require 2-3 visits per week for 10-12 weeks, are onerous for many patients. This may be even more difficult for patients with mobility limitations, which are common after stroke. Third, the cost of CBT may be prohibitive, particularly if providers do not accept insurance.⁶ Finally, patients may be resistant to in-person CBT because of stigma or fear of sharing deeply personal feelings with a therapist.

Technology and CBT

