- Patients without regular internet access through a computer, tablet or smartphone are excluded.
- Subjects requiring long-term inpatient nursing care are excluded. For patients enrolled as inpatients, individuals being discharged to both home and acute rehab are eligible. Individuals being discharged to a skilled nursing facility or hospice are excluded.
- Expected life expectancy less than 6 months or other inability to comply with study follow-up.
- Pregnant women and prisoners are excluded

Vulnerable populations: Children, pregnant women, fetuses, neonates, and prisoners are not included in this research study.

Sample Size: 20 subjects will be enrolled.

Accrual: The comprehensive stroke center at the Hospital of the University of Pennsylvania (HUP) is a tertiary referral center for acute ischemic stroke, with annual case volumes of approximately 600 strokes per year on the inpatient stroke service. Additionally, the stroke team sees patients in the outpatient clinic both in follow-up from their acute hospitalization and in consultation to provide second opinions for patients treated elsewhere. Due to the broad inclusion criteria of this study, it is expected that many of the patients seen, both inpatient and outpatient, will be eligible for participation in this study. We expect that we will be able to enroll 1-2 patients per week and will complete enrollment within 6 months.

Recruitment: A stroke physician evaluates all patients with acute ischemic stroke who present to HUP. All stroke team physicians will be trained investigators in this study, and they will screen patients for eligibility during routine clinical care. Study physicians will also screen for potentially eligible subjects during outpatient clinic sessions. All eligible subjects will be informed of the study, and if they are interested in participation, a study physician will obtain informed consent. The original signed consent form will be kept in the study binder. A copy of

the signed consent form will be given to the patient and another copy will be placed in the medical record.

Procedures

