For patients who are enrolled, basic demographic and clinical information will be collected including: age, sex, race/ethnicity, past medical history (including history of hypertension, hyperlipidemia, coronary artery disease, chronic kidney disease, prior history of TIA/Stroke, prior history of anxiety, depression, or PTSD, other medical history), educational attainment, insurance status, marital status, number of people living in the home, medication history (current/prior use of an antidepressant medication), current/prior participation in psychotherapy or counseling for mental health problems, tobacco history (current smoker, former smoker, never smoker), alcohol use history (current alcohol use yes/no and if yes, number of drinks per week), stroke location, stroke mechanism (large vessel atherosclerosis, small vessel disease, cardioembolism, other, cryptogenic), discharge disposition (home, acute rehab).

Additional assessments will include the NIHSS, a structured neurologic examination used to quantify neurologic deficits,^{16, 17}, modified Rankin Scale,¹⁸ the Patient Health Questionnaire-9 (PHQ-9) to assess mood,¹⁵ and the abbreviated Duke Social Support Index.¹⁹ We will also ask the subject a series of questions regarding availability of internet and mobile device usage, including how they interact with the internet and frequency of internet use (See attached appendix).

After baseline data collection, the subjects will be enrolled in Joyable's iCBT program. For subjects who would like to participate in the program using their smartphone, the CBT application will be installed on their device and they will be encouraged to complete the initial

evaluation and activities at the time of enrollment. Subjects without their own device will be enrolled via a study specific tablet using the web-interface. Subjects will be given their login information and information on how to access the program via the internet and install the program on their mobile device. Subjects will be asked to complete the initial evaluation and CBT activities at the time of enrollment.

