Subjects will be seen by the study team 90 days +/- 14 days after enrollment to assess their neurologic function using the NIHSS, mood using the PHQ-9, functional status using the modified Rankin Scale, Quality of life using the Euroqol EQ-5D,^{20, 21} healthcare utilization using the Stanford Health Utilization survey,²² whether any other treatment for mental health problems was received (including medication and psychotherapy) and perceived utility of Joyable iCBT for depression as well as perceived barriers to successful use of internet-based CBT.

Table 1. Study measures and timing of assessment

	Baseline	72 hr Call	30 day call	90 day visit
Demographics	X			
Stroke information	X			
SSRI Use	X		X	X
Assess for technical problems		X	X	
NIHSS	X			X
mRS	X		X	X
EQ-5D	X		X	X
SHU				X
PHQ-9	X			X
Semi-Quantitative assessment of perceptions about Internet-based CBT				X

NIHSS=National Institute of Health Stroke Scale, EQ-5D=Euro-Qol 5D, SHU=Stanford Health Utilization survey, PHQ-9=Patient Health Questionnaire 9,

Analysis Plan

The baseline demographic variables of the study population will be summarized using means, medians, and proportions as appropriate. For each subject, we will calculate the total amount of time spent interacting with the Joyable program and the total number of Joyable activities that the patient successfully completed. We will then calculate averages across the study population. These metrics will provide important information on the average “dose” of CBT received. In an exploratory analysis we will look for relationships between baseline clinical and demographic factors and number of activities completed.

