We will calculate the average PHQ-9 score at enrollment and 90 days. We will compare the PHQ-9 score from enrollment to day 90. The statistical power of this test is uncertain. In Table 2 we present estimated study power (with $\alpha=0.05$) across a range of assumptions about both the change in PHQ-9 over time and the standard deviation of the difference in PHQ-9 over time. These calculations show that although this is a small pilot study, we have >80% power to detect a difference in PHQ-9 of 3 or more points across a range of assumptions. The PHQ-9 will also be administered to subjects weekly via through the Joyable program. We will examine whether there are significant changes in score over time using repeated measures analysis (generalized estimating equations, GEE) with PHQ-9 score as the dependent variable and week as the independent variable.

In an exploratory analysis, we will divide patients into two groups based on PHQ-9 at study completion (*high depression symptoms*, defined as median or above and *low depression*

symptoms, defined as below the median score). Healthcare outcomes, including modified Rankin scale, health related quality of life, and healthcare utilization will be compared across groups. We hypothesize that patients with high depression symptoms will have worse functional outcome, lower quality of life, and higher healthcare utilization. We will also divide patients into groups based on their participation in the Joyable program and compare outcomes (e.g., PHQ-9 score, quality of life, health utilization) between subjects who showed high engagement in the program and those who showed low engagement.

Table 2. Statistical Power for single sample paired t-test

SD of the Difference	Difference in PHQ-9 Pre/Post Treatment				
	1	2	3	4	5
2	61%	99%	100%	100%	100%
3	32%	85%	99%	100%	100%
4	20%	61%	92%	99%	100%
5	15%	43%	77%	95%	99%
6	12%	32%	61%	85%	96%

Data Confidentiality

Internet-based files will only be made available to personnel involved in the study through the use of access privileges and passwords. Paper-based records will be kept in a locked, secure location and only accessible to study personnel. Prior to access to any study-related information, personnel will be required to sign statements agreeing to protect the security and confidentiality of identifiable information. Whenever feasible, identifiers will be removed from study-related information.

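### The 90-day utilization form asks about overnight stays over six months under a since-enrolment heading, so the count can reach 76 to 104 days before enrolment and take in the index stroke admission

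*Combined protocol and SAP*

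**What the plan says.** The Secondary Outcome variables section lists "healthcare utilization, measured using the Stanford Health Care Utilization Survey". The Analysis Plan uses it in exploratory work: "Healthcare outcomes, including modified Rankin scale, health related quality of life, and healthcare utilization will be compared across groups", the groups being a median split on the final PHQ-9. It also names utilization as an outcome for the comparison of high and low engagement.

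The instrument is item 5 of the 90 Day Visit CRF in the Appendix. Its four questions (physician visits, emergency-room visits, overnight stays, total nights) sit under the heading "Since study enrollment". The first two carry no window of their own. The overnight-stay question adds "or longer in the past 6 months". The nights question gives no window.

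On timing, the 90 Day In-person Visit section states: "Subjects will be seen by the study team 90 days +/- 14 days after enrollment". Table 1 schedules the utilization survey at that visit only.

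On who enters, the Target Population is patients hospitalized with ischemic stroke. The Inclusion Criteria cap the time since stroke (printed as 63 months) but set no minimum. The Exclusion Criteria allow enrolment during the admission: "For patients enrolled as inpatients, individuals being discharged to both home and acute rehab are eligible".

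**The concern.** One question carries two recall periods. The heading limits it to follow-up, whereas the wording the subject actually answers reaches back past enrolment. In this population the event most likely to lie in the extra stretch is the qualifying stroke admission, which is not an outcome of the study.

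Whether that admission is counted then depends on how long after the stroke the subject enrolled and on which window the subject follows. The survey has no baseline administration to subtract, and it records counts without dates. The form alone therefore cannot separate stays before enrolment from stays after it. The nights question may be read with either window, so stays and nights from the same subject may cover different periods.

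**Working it through.** The plan states no figure for this recall period, so there is none to reproduce. The check is day arithmetic, followed by a sensitivity calculation on assumed values.

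**1. Can the two windows agree?** Inputs: a visit at 90 ± 14 days after enrolment, that is day 76 to day 104 (90 Day In-person Visit section), and six months taken as 180 days.

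Reach before enrolment = 180 − visit day.

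| Visit day | Days before enrolment | Share of the 180 days |
|---|---|---|
| 76 | 180 − 76 = 104 | 104/180 = 58% |
| 90 | 180 − 90 = 90 | 90/180 = 50% |
| 104 | 180 − 104 = 76 | 76/180 = 42% |

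Six calendar months run 181 to 184 days. This lengthens each reach by 1 to 4 days, giving 77 to 108 days overall. No permitted visit day brings the reach to zero.

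**2. Who can be affected?**

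- *Enrolled as an inpatient:* the index admission is always inside the six-month window. It also straddles enrolment, so even the heading does not settle whether that stay and its remaining nights count. This is a separate gap, which would remain if the six-month phrase were removed.
- *Enrolled after discharge, with the admission inside the 76 to 104 days before enrolment (depending on visit day):* the admission is counted if the subject follows the item, and not if the subject follows the heading.
- *Enrolled later than that:* the index admission is outside both windows. Any other stay in the pre-enrolment stretch could still be counted under the item.

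**3. What can be recovered from the data?** Item 9 of the Baseline CRF ("Witnessed onset Last known normal") has a date field for stroke onset, and the 90-day form carries the visit date. An interval of about 180 days or less flags a likely case. It does not show which window the subject used.

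**4. How large could the error be?** The documents give neither the share enrolled early nor how subjects read the item. Assume a true mean of *m* = 0.2 to 0.3 stays per subject (4 to 6 stays in 20 subjects). Let *f* be the share who enrolled early, answer by the item and so add one stay.

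Inflation of the mean = (m + f)/m = 1 + f/m.

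| f | Subjects of 20 | m = 0.3 | m = 0.2 |
|---|---|---|---|
| 0 | 0 | 1.00 | 1.00 |
| 0.05 | 1 | 1.17 | 1.25 |
| 0.25 | 5 | 1.83 | 2.25 |
| 0.50 | 10 | 2.67 | 3.50 |

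One affected subject moves the overall mean by 1/20 = 0.05 stays. In a group of 10 the shift is 1/10 = 0.10 stays, which is 0.10/0.3 = 33% to 0.10/0.2 = 50% of the assumed mean.

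**The case against.** The strongest reply is that the heading governs and that staff, who see the subject at this visit, can explain the window. That is possible, but no document says so and the form gives staff no instruction. The more specific period is printed inside the question itself. The pre-enrolment reach does apply only when the item wording is followed, and the size of the error depends on that.

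A second reply is that the inflation factors rest on assumed values. This is correct. Neither *m* nor *f* has a source in the documents, and with a 63-month eligibility window and outpatient recruitment *f* could be small or zero. Only the day arithmetic is tied to the plan.

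A third is that bias in the group comparisons is not shown. This also stands. If affected subjects fall evenly across groups of equal size, both means rise and the difference does not change. The difference is distorted only by an uneven split, and its direction cannot be predicted. Groups of exactly 10 are not assured either: the upper group includes scores at the median, so ties can unbalance the split, and the engagement groups have no stated cut-off.

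Finally, this is one question in a secondary outcome of a 20-subject single-arm pilot. That limits the consequence but does not remove the contradiction.

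**Conclusion.** The concern holds. The overnight-stay item contradicts its own heading at every permitted visit day. As worded it reaches 104 to 76 days before enrolment, and it can count the qualifying stroke admission as an outcome. That conclusion needs only the visit window and 180 days for six months; calendar months do not change it.

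The effect on the results is unknown. It depends on the share of subjects enrolled early and on which window they follow, and it may be nil. It is confined to the stays count, and possibly the nights count, within a secondary outcome used in exploratory comparisons. Physician and emergency-room visits have no competing window. The primary outcomes and the power figures in Table 2 are unaffected. It should be fixed because the wording is wrong as it stands, the undated counts cannot be separated afterwards from the form alone, and the correction is nearly free.

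**What to change.** For the form:

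- Delete the six-month phrase so that all four questions use the since-enrolment window, and print the enrolment date on the form.
- On the stays and nights questions, state that the stroke admission during which the subject joined the study is not counted. This is a counting choice, so it should be written down.
- State whether an acute-rehabilitation stay counts as a hospital stay. For someone enrolled as an inpatient, that stay begins after enrolment and would otherwise be handled inconsistently.

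For forms already completed:

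- Flag subjects whose stroke onset was within about 180 days of the 90-day visit.
- Check all reported stays against available medical records, starting with the flagged subjects. Onset date alone can miss an admission that began before the 180-day point and ended inside it, so the check should not stop at the flagged subjects.
- Count only stays, with their nights, that began after enrolment, and apply the acute-rehabilitation rule.
- Report how many counts were changed.

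The cost is a minor CRF amendment and record checking in at most 20 subjects. Stays at other hospitals may not appear in the available records; counts that cannot be verified should be reported as such.
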